#### **4.2.3. Elimination from unsolicited and solicited safety set**

##### **4.2.3.1. Excluded subjects**

###### **4.2.3.1.1. Unsolicited safety set**

Code 1030 (Study vaccine not administered at all), code 800 (fraudulent data) and code 900 (invalid informed consent) and code 1150 (no post-vaccination safety data) will be used for identifying subjects eliminated from the unsolicited safety set.

###### **4.2.3.1.2. Solicited safety set**

Code 1030 (Study vaccine not administered at all), code 800 (fraudulent data) and code 900 (invalid informed consent) and code 1160 (no post-vaccination solicited safety data) will be used for identifying subjects eliminated from the solicited safety set.

### **5. STATISTICAL ANALYSES**

Standard data derivation rules and statistical methods are described in section 10.1 while the study specific data derivation rules and stat methods are described in section 9.

#### **5.1. Disposition of subjects**

##### **5.1.1. Analysis of disposition of subjects planned in the protocol**

Number of subjects enrolled, vaccinated subjects (at least 1 vaccination, full vaccination course), reason for early withdrawal, FAS, and PPS will be described by vaccine group.

##### **5.1.2. Additional considerations**

Not applicable

## **5.2. Demography and baseline characteristics analyses**

### **5.2.1. Analysis of demography and baseline characteristics planned in the protocol**

Descriptive statistics (mean, standard deviation, median, minimum and maximum) for age, height, weight, and body mass index (BMI) at enrolment will be calculated overall and by vaccine group.

Distributions of subjects by sex, race, ethnic origin will be summarised overall and by vaccine group.

### **5.2.2. Additional considerations**

A summary table of important protocol deviations related to COVID-19 will be provided. Also, a listing will be produced.

## **5.3. Primary effectiveness and immunogenicity**

### **5.3.1. Analysis of primary effectiveness and immunogenicity planned in the protocol**

Refer to Glossary of terms for definitions of test-based and responder-based vaccine effectiveness. If the co-primary effectiveness objectives for rMenB+OMV NZ are met (Sections 5.3.1.1 through 5.3.1.6), then all objectives for MenACWY will be evaluated at 95% CI (Sections 5.3.1.7 through 5.3.1.11, ref Protocol Section 10.1).

#### **5.3.1.1. Vaccine effectiveness (Test-based): rMenB+OMV NZ - 3 doses (0,2,6-months schedule)**

Analysis set: Per-protocol set (PPS) will be the primary analysis population

Statistical method: The VE is defined as  $1 - RR = (1 - \text{percentage of samples without bactericidal serum activity at 1:4 dilution in MenB group} / \text{percentage of samples without bactericidal serum activity at 1:4 dilution in the ACWY group}) \times 100\%$  and it will be analyzed using a generalised linear model with vaccine group, strain, and randomization factors (i.e. region (US/ex-US), age category (10-17 YoA/18-25 YoA), previous MenACWY vaccination (y/n)) as independent variables. Furthermore, a repeated statement will be used to estimate the variance of the RR including correlation within subject's responses to different strains. If the statistical model does not converge due to (one of) the factor(s), a model without this/these factor(s) will be fitted instead. The response variable of the model will be the Bernoulli distributed outcome without bactericidal activity at a 1:4 dilution (i.e. response is 1 if titre  $< 4$ , and 0 if titre  $\geq 4$ ), at 1 month after the last vaccination (Month 7) in the MenB group and at Month 1 for the ACWY group. Each subject will contribute with approximately 35 measures to this analysis, each of the measures corresponding to the response variable to one of the 35 strains randomly assigned to be tested with the samples available for that specific subject.

In order to obtain the VE measure which is a measure based on the relative risk (RR), a generalised linear model will be used with the Binary distribution and link function log in order to compute the log RR and the corresponding 97.5% CI. The obtained values will be exponentiated to obtain the RR and the corresponding 97.5% CI. The VE will be computed as  $100\% \times (1 - RR)$ . Effectiveness of rMenB+OMV NZ (0,2,6-months schedule) will be demonstrated if the lower limit of the two-sided 97.5% CI for VE between MenB and the ACWY group is above 65%.

**5.3.1.2. Effectiveness (Responder-based): rMenB+OMV NZ - 3 doses (0,2,6-months schedule)**

Analysis set: FAS will be the primary analysis population.

Statistical method: The percentage of responders (see definition in Glossary of terms) and the corresponding exact two-sided 97.5% CI based on Clopper-Pearson method will be calculated [Clopper, 1934].

The objective is to demonstrate that the lower limit of the 97.5% CI for the percentage of responders is higher than 65%.

**5.3.1.3. Vaccine effectiveness (Test-based): rMenB+OMV NZ - 2 doses (0,6-months schedule)**

See Section 5.3.1.1

**5.3.1.4. Effectiveness (Responder-based): rMenB+OMV NZ - 2 doses (0,6-months schedule)**

See Section 5.3.1.2

**5.3.1.5. Vaccine effectiveness (Test-based): rMenB+OMV NZ - 2 doses (0,2-months schedule)**

See Section 5.3.1.1

**5.3.1.6. Effectiveness (Responder-based): rMenB+OMV NZ - 2 doses (0,2-months schedule)**

See Section 5.3.1.2

**5.3.1.7. Lot-to-lot consistency: MenABCWY - ACWY component**

Analysis set: The analysis of lot-to-lot consistency will be based on the PPS.

Statistical method: For each of the three ABCWY lots (Lots 1, 2 and 3 of the MenACWY component of the ABCWY vaccine), GMTs and 97.5% CIs will be calculated by exponentiating (base 10) the least squares means and the lower and upper limits of the 97.5% CIs of the log transformed titres (base10) obtained from an Analysis of Variance

(ANOVA) with factors for vaccine lot and randomization factors (i.e. region (US/ex-US), age category (10-17 YoA/18-25 YoA), previous MenACWY vaccination (y/n)).

Additionally, lot-to-lot GMT ratios will be computed for each pair of ABCWY lots.

Ninety-seven point five percent (97.5%) CIs for the ratios of GMTs will be constructed by exponentiating the difference of the least square means of the log transformed titres and the lower and upper limits of the 97.5% CIs on the difference obtained from the ANOVA model above.

**Lot-to-lot consistency criterion:** The three ABCWY lots will be considered equivalent if for each of the 4 serogroups A, C, W and Y and each pair of vaccine lots, the two-sided 97.5% CI on the ratio of GMTs at 1 month after the last vaccination will be contained within the interval [0.5, 2.0].

If the co-primary effectiveness objectives for rMenB+OMV NZ are met (Sections 5.3.1.1 through 5.3.1.6), then the above will be evaluated at 95% CI.

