##### Rationale for lot-to-lot consistency assessment

MenABCWY is a reconstituted vaccine with the lyophilised 'ACWY component' and liquid\_rMenB+OMV NZ. The MenB component has the same formulation as the commercial *Bexsero*. To demonstrate that the lots of the investigational MenABCWY vaccine are adequately representative of the formulation intended for marketing, equivalence will be assessed for 3 different lots of the ACWY component of the ABCWY vaccine.

Rationale for non-inferiority assessment of MenABCWY vs MenACWY and rMenB+OMV NZ

The study aims to also demonstrate that the investigational combination MenABCWY vaccine is not inferior to a licensed MenACWY vaccine (*Menveo*) and a licensed MenB vaccine (*Bexsero*) which are part of the current standards of care in the US for prevention of invasive disease caused by *N. meningitidis* serogroups A, C, W, Y and by *N. meningitidis* serogroup B, respectively.

Rationale for blood volume collected:

In order to provide the necessary serum volume for the bactericidal assays (enc-hSBA and/ or hSBA(s)), 25 mL whole blood will be collected at Visit 2, Visit 4 and Visit 6. At pre-vaccination (Visit 1), 20 mL whole blood will be collected to provide the necessary serum volume for the hSBA.

Blood samples are taken from all subjects irrespective of the testing status in order to maintain the study blind. Refer to Protocol Section 8.4.2.1 for further details.

Rationale for the selected vaccination schedules

rMenB+OMV NZ: This study aims at demonstrating the VE of the rMenB+OMV NZ vaccine administered as 2-dose vaccine, either with a shorter interval (0,2-months) or a prolonged interval (0,6-months) between doses. A 3-dose schedule has been also added to better characterise the VE.

Note: The rMenB+OMV NZ in the ACWY group is administered in a 0,1-months schedule. This interval is within the recommendations in the summary of product characteristics of *Bexsero* and helps in maintaining the blind. No objectives are associated with this schedule of rMenB+OMV NZ.

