### **3.3. Number of subjects**

A total of 3651 subjects will be randomised in a ratio of 5:5:3:3:3:1; 912 each in MenB\_0\_2\_6 and MenB\_0\_6 groups, 548 in each ABCWY groups and 183 in ACWY group. Assuming a 25% drop out rate, this should provide approximately 684 evaluable subjects in each of the MenB groups, 411 evaluable subjects in each of the ABCWY groups and 137 evaluable subjects in the ACWY group.

Refer to Protocol Section 10.1 for a detailed description of the criteria used in the determination of sample size.

Withdrawals will not be replaced.

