**5.4.1.4. Immune response of MenABCWY, rMenB+OMV NZ and MenACWY**

Analysis set: The analysis will be based on the FAS.

Statistical method: The hSBA titres at each time point for all groups (ABCWY group (pooled lots), MenB\_0\_2\_6 and MenB\_0\_6 groups) will be logarithmically transformed (base10) to fulfil the normal distribution assumption. For each *N. meningitidis* serogroup A, C, W and Y and each B indicator strain (M14459, 96217, M07-0241084\* and NZ98/254 for fHbp, NadA, NHBA and PorA P1.4 antigens, respectively), the GMTs and GMRs (post-vaccination/baseline) will be obtained from an Analysis of Variance (ANOVA) with factors for vaccine group, region (US/ex-US), age category (10-17 YoA/18-25 YoA), and previous MenACWY vaccination (y/n), and then exponentiating the log-transformed means and their 95% CIs. The ratio of GMTs and GMRs between two groups and the corresponding CI will be estimated additionally.

The total IgG (as measured by ECL) against serogroups A, C, W and Y at baseline (Day 1, Month 0) and

- at 1 month after the first (Day 31, Month 1) and the last vaccination (Day 211, Month 7) for the ABCWY group (pooled lots), and
- at 1 month after the MenACWY vaccination in the ACWY group (Day 31, Month 1),

will be analyzed in a comparable way as described above for hSBA titres. Since total IgG is measured as concentration instead of titer, the resulting geometric mean of the concentrations is abbreviated as GMC.

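### Lot-to-lot and post-vaccination GMT models leave out the pre-vaccination titre, a nearly free precision gain; the analysis is valid as it stands

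*SAP*

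**What the plan says.** **Lot consistency (SAP 5.3.1.7, primary objective).** Log10 titres at Month 7 are analysed by "ANOVA) with factors for vaccine lot and randomization factors (i.e. region (US/ex-US), age category (10-17 YoA/18-25 YoA), previous MenACWY vaccination (y/n"). The lots are equivalent if, for every lot pair and every serogroup, "the two-sided 97.5% CI on the ratio of GMTs at 1 month after the last vaccination will be contained within the interval [0.5, 2.0"]. Should all rMenB+OMV NZ objectives be met, "then the above will be evaluated at 95% CI". The wording is the same in Amendments 2, 3 and 4.

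**Immune response (SAP 5.4.1.4, secondary).** Here "the GMTs and GMRs (post-vaccination/baseline) will be obtained from an Analysis of Variance (ANOVA) with factors for vaccine group, region (US/ex-US") and the other two strata. Between-group ratios of GMTs and of GMRs are estimated as well, and IgG concentrations are handled in a comparable way.

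**Baseline titre.** Section 3.1 says of the pre-vaccination visit that "20 mL whole blood will be collected to provide the necessary serum volume for the hSBA". Table 1 lists Day 1 A, C, W and Y titres in the ABCWY groups as endpoints (percentage at or above LLOQ, GMT, and the denominator of the GMR), and the 4-fold rise in 5.3.1.8 needs them. No baseline-adjusted analysis appears elsewhere: the additional-considerations sections 5.3.2.7 and 5.4.2.4 are marked not applicable. The first SAP version (25 July 2019) allowed an optional ANCOVA on baseline titre for possible imbalance. The later versions shown no longer have it and give no reason.

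**The concern.** The pre-vaccination titre is fixed before randomised treatment starts, is already planned to be assayed in the groups concerned, and would ordinarily correlate with the post-vaccination titre. Leaving it out keeps variance in the residual that could be removed at no cost in data.

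The lot criterion is demanding. Twelve intervals (4 serogroups x 3 lot pairs) must all lie within the limits, so any avoidable width counts twelve times. It is a primary objective within a testing scheme that stops at the first hypothesis not rejected (SAP section 6).

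**Working it through.** **Inputs from the SAP.** "A total of 3651 subjects will be randomised in a ratio of 5:5:3:3:3:1" (section 3.3), with 548 per lot and 25% dropout. The limits 0.5 to 2.0 are ±0.301 on the log10 scale. The CI is two-sided 97.5% (z = 2.241), or 95% (z = 1.960) if alpha is passed on.

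**Assumed, because the SAP gives no value.** SD of log10 titre within strata 0.4 to 1.2; baseline-post correlation within strata, rho, 0.3 to 0.7.

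**Step 1: the plan's own figure.** 548 x 0.75 = 411 evaluable per lot, as stated in section 3.3.

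**Step 2: gain from the covariate.** The residual SD is multiplied by sqrt(1 - rho²). The equivalent gain in sample size is 1/(1 - rho²) - 1.

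| rho | SE falls by | equals extra subjects |
|---|---|---|
| 0.3 | 5% | 10% |
| 0.4 | 8% | 19% |
| 0.5 | 13% | 33% |
| 0.6 | 20% | 56% |

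**Step 3: against the limits.** The SE of a log10 GMT ratio is SD x sqrt(2/411) = 0.0698 x SD. For SD 0.8 the 97.5% half-width is 2.241 x 0.0698 x 0.8 = 0.125, a factor of 1.334. With rho 0.5 it is 0.125 x 0.866 = 0.108, a factor of 1.283.

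The table gives the probability that all 12 intervals pass (simulation, 100,000 runs, serogroups independent, 97.5% CI), without the covariate and then with it at rho 0.5. In the last column one lot differs from the other two by a true ratio of 1.25 in every serogroup.

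| SD | CI factor | identical lots | one lot at 1.25 |
|---|---|---|---|
| 0.4 | 1.155 to 1.133 | 100% to 100% | 100% to 100% |
| 0.6 | 1.241 to 1.206 | 100% to 100% | 96.8% to 99.8% |
| 0.8 | 1.334 to 1.283 | 98.2% to 99.9% | 56.2% to 83.8% |
| 1.0 | 1.433 to 1.366 | 67.0% to 93.5% | 14.0% to 38.7% |
| 1.2 | 1.540 to 1.454 | 16.0% to 55.7% | 1.9% to 9.9% |

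At the 95% CI the pattern is the same with smaller gaps: for SD 1.0 and identical lots, 82.1% to 97.1%; for SD 0.8 with one lot at 1.25, 71.8% to 91.4%.

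**Step 4: chance imbalance.** The 95% range of the shift that baseline imbalance can put into one pairwise ratio is 10^(1.96 x rho x SD x sqrt(2/411)). This is 1.04 (SD 0.4, rho 0.3), 1.13 (SD 0.8, rho 0.5) and 1.30 (SD 1.2, rho 0.7). The unadjusted CI already allows for this spread; the covariate removes it from the estimate.

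**Step 5: GMRs.** A GMR model fixes the slope on baseline at 1, and the GMT model fixes it at 0. With equal variances the variance of the log change is 2(1 - rho) x SD², which exceeds SD² whenever rho is below 0.5. An estimated slope gives (1 - rho²) x SD², no larger than either.

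**The case against.** The strongest reply is that nothing here is wrong. Lots are randomised, the contrast is unbiased, its interval covers chance imbalance, and all three randomisation factors are in the model. That stands. A reader might infer that baseline imbalance biases the lot comparison; the design rules that out.

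Several other tempting readings also go too far.

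- **Baseline measured on every subject.** Section 3.1 says blood is drawn from all subjects whatever their testing status. Universal sampling is stated, universal testing is not. What is supported is that Day 1 A, C, W and Y titres are endpoints in the ABCWY and ACWY groups.
- **Baseline as the strongest predictor.** The SAP does not show this. Previous MenACWY vaccination, age and region already absorb part of the baseline variation. All values below the cut-off collapse to half the cut-off, which limits what the covariate can explain.
- **An underpowered primary objective.** No SD, correlation or lot-to-lot power is given; section 3.3 refers sample size to the protocol. For an SD up to 0.6 and identical lots the criterion passes practically always without the covariate.
- **A failed lot test stopping every MenABCWY objective.** Lot consistency comes first in section order, but the testing order is set by Figure 2, which is not shown.
- **Baseline ignored in 5.4.1.4.** GMRs already divide by it, and that section carries no success criterion.

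Finally, the quoted text is Amendment 4. Amendment 5 is later and its 5.3.1.7 is not in the part at hand. Its visible parts add no baseline-adjusted analysis (5.4.2.4 and 9.2 are marked not applicable), but the current lot model has to be checked.

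These points limit the claim. They do not answer why a covariate already planned to be assayed is left out of an equivalence model.

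**Conclusion.** The point holds as one of efficiency. In Amendments 2 to 4 the lot-to-lot ANOVA and the post-vaccination GMT and GMC comparisons omit log10 baseline titre, and including it would narrow the intervals. For an assumed within-strata correlation of 0.3 to 0.6 the SE falls by about 5% to 20%, worth 10% to 56% more subjects per lot. The effect on the lot criterion depends on an SD that the SAP does not give: negligible up to about 0.6 log10 with similar lots, material from about 0.8 to 1.0 upwards or when lots truly differ. Validity is not in question. The change is worth making because it costs almost nothing, subject to confirming the wording of Amendment 5.

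**What to change.** 1. In 5.3.1.7, add log10 pre-vaccination titre for the same serogroup as a continuous covariate beside lot and the three strata. If the primary model is to stay unchanged, specify this ANCOVA as a sensitivity analysis.
2. In 5.4.1.4, add the covariate to the post-vaccination between-group GMT and GMC ratios only. It has no place in the summaries of baseline GMTs.
3. With log baseline as covariate, the adjusted between-group ratios of GMTs and of GMRs are the same number. Report one adjusted ratio and keep the within-group GMRs as descriptive summaries.
4. Use the existing half-cut-off rule (10.1.3.8 and 10.1.3.9) for low baselines.
5. Section 10.1.2.2 says missing laboratory results are not replaced. State an exception for the covariate alone, for example filling a missing baseline with the overall mean without regard to lot, so that no subject drops out of the model.

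The cost is one model term and two sentences of text, with no new data. It should be fixed before unblinding.

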#### **5.3.1.8. Immunological non-inferiority: MenABCWY vs. MenACWY**

**Analysis set:** PPS restricted to subjects without previous ACWY vaccination will be the primary analysis population.

**Statistical method:** The percentage of subjects with 4-fold rise\* in hSBA titres against MenACWY indicator strains A, C, W and Y and the corresponding exact two-sided 97.5% CIs based on Clopper-Pearson method will be calculated for the ABCWY (pooled lots) group and the ACWY group [Clopper, 1934]. The 97.5% CIs for the difference in percentages between ABCWY (pooled lots) and ACWY group will be constructed using the method of Miettinen and Nurminen [Miettinen, 1985].

**Non-Inferiority criterion:** Non-inferiority of MenABCWY vaccine for the proportion of subjects with 4-fold rise will be demonstrated if the lower limit of the two-sided 97.5% CI for the difference in percentage of subjects with 4-fold rise between the 2 groups (ABCWY (pooled) lots –ACWY) is above -10%.

\* For the Men A, C, W, Y evaluation, the 4-fold rise is defined as:

- a post-vaccination hSBA titre  $\geq 4$  times the LOD for subjects with a pre-vaccination hSBA titre  $< \text{LOD}$
- a post-vaccination hSBA titre  $\geq 4$  times the LLOQ for subjects with a pre-vaccination hSBA titre  $\geq \text{LOD}$  but  $< \text{LLOQ}$ , and
- a post-vaccination hSBA titre  $\geq 4$  times the pre-vaccination titre for subjects with a pre-vaccination hSBA titre  $\geq \text{LLOQ}$ .

Table 5 reads the LOD and LLOQ of MenACWY indicator strains used in the definition of 4-fold rise provided by the laboratory.

**Table 5 LOD and LLOQ of MenACWY indicator strains**

Strain	LOD	LLOQ
Men A (3125)	CCl	
Men C (C11)		
Men W (240070)		
Men Y (860800)		

If the co-primary effectiveness objectives for rMenB+OMV NZ are met (Sections 5.3.1.1 through 5.3.1.6), then the above will be evaluated at 95% CI.

#### **5.3.1.9. Vaccine effectiveness (Test-based): MenABCWY**

See Section 5.3.1.1. If the co-primary effectiveness objectives for rMenB+OMV NZ are met (Sections 5.3.1.1 through 5.3.1.6), then the VE for MenABCWY will be evaluated at 95% CI.

#### **5.3.1.10. Effectiveness non-inferiority: MenABCWY vs. rMenB+OMV NZ**

Analysis set: PPS will be the primary analysis population.

Statistical method: The percentage of samples with bactericidal activity measured by enc-hSBA at 1:4 dilution and the corresponding exact two-sided 97.5% CIs based on Clopper-Pearson method will be calculated for the ABCWY (pooled lots) group and the MenB group comparator that will be selected (ref: the footnote of Figure 2). The 97.5% CIs for the difference in percentages between ABCWY (pooled lots) and selected MenB group will be constructed using the method of Miettinen and Nurminen [Miettinen, 1985].

Non-Inferiority criterion: Non-inferiority of MenABCWY vaccine for the percentage of samples with bactericidal activity measured by enc-hSBA at 1:4 dilution will be demonstrated if the lower limit of the two-sided 97.5% CI for the difference between the 2 groups (ABCWY (pooled) lots – MenB) is above -5%.

If the co-primary effectiveness objectives for rMenB+OMV NZ are met (Sections 5.3.1.1 through 5.3.1.6), then the above will be evaluated at 95% CI.

#### **5.3.1.11. Effectiveness (Responder-based): MenABCWY**

See Section 5.3.1.2. If the co-primary effectiveness objectives for rMenB+OMV NZ are met (Sections 5.3.1.1 through 5.3.1.6), then the effectiveness (responder-based) for MenABCWY will be evaluated at 95% CI.

### 5.3.2. Additional considerations

Analyses of the primary effectiveness and immunogenicity objectives will be repeated by age group (10-17 years of age and 18-25 years of age), race, sex, region (US/ ex-US), and subjects with and without a previous MenACWY vaccination (primed and unprimed).

#### 5.3.2.1. Vaccine effectiveness (Test-based): rMenB+OMV NZ - 3 doses (0,2,6-months schedule)

The SAS code to analyse the Vaccine effectiveness (Test-based): rMenB+OMV NZ - 3 doses (0,2,6-months schedule) objective is specified below. Treatment, region, age category, previous ACWY vaccination, and strains will be modelled as fixed effect. To account for a possible over-dispersion, the DSCALE option in the model statement will be evaluated first. The DSCALE will be kept in the model only if the F-statistics for the DSCALE parameter is significant ( $p<0.05$ ). The following SAS code will be used for the VE calculation:

```

ods trace on;
ods output GEEmpPEst = genmod_stats
CONVERGENCESTATUS = converge ;

PROC GENMOD data=dataset descending;
class trtgrp strain region agecat previousACWY subject_id ;
model outcome = trtgrp strain region agecat previousACWY / dist= bin
link= log DSCALE;
repeated subject = subject_id / type= CS withinsubject= strain;
estimate 'MenB026-ACWY' trtgrp 1 0 0 0 0 -1/ alpha=0.025 exp;

/*trtgrp R is MenB0,2,6 and trtgrp W is ACWY*/

run;

ods output close;

data genmod_stats;
set genmod_stats;
where parm = 'trtgrp' and level1 = '1';
rr = exp(estimate);
ub = exp(uppercl);
ve = (1 - rr)*100 ;
ve_ll = (1 - ub) * 100 ;
if ve_ll > 65 then success = 1 ;
else success = 0 ;
run;

```

where outcome represents the Bernoulli distributed outcome without bactericidal activity at a 1:4 dilution (i.e. response is 1 if titre  $< 4$ , and 0 if titre  $\geq 4$ ), one month after the 3rd vaccination in MenB 0,2,6 and one month after the MenACWY vaccination for the ACWY arm, trtgrp indicates the vaccine groups, strain is the serogroup B strain variable, region is either US or ex-US, agecat is the age at enrolment (10-17 YoA or 18-25 YoA), and previousACWY is previous ACWY vaccination (y/n) at enrolment.

rr is the relative risk (RR), which is obtained from the estimated parameters from PROC GENMOD. Vaccine effectiveness (VE) is then derived as (1-rr)x100%.

ub represents the upper bound of the 97.5% CI of the relative risk. ve\_ll is the lower bound of the 97.5% CI for VE, if the value is greater than 65%, then the Vaccine effectiveness (Test-based): rMenB+OMV NZ - 3 doses (0,2,6-months schedule) objective is successful.

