#### **5.3.2.3. Vaccine effectiveness (Test-based): rMenB+OMV NZ - 2 doses (0,6-months schedule)**

See Section 5.3.2.1, with the difference in the treatment arm:

```
PROC GENMOD data=dataset descending;
class trtgrp strain region agecat previousACWY subject_id ;
model outcome = trtgrp strain region agecat previousACWY / dist= bin
link= log DSCALE ;
repeated subject = subject_id / type= CS withinsubject= strain ;
estimate 'MenB06-ACWY' trtgrp 0 1 0 0 -1/ alpha=0.025 exp;
/*trtgrp S is MenB0,6 and trtgrp W is ACWY*/
run;
```

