### 5.3.2.9. Vaccine effectiveness (Test-based): MenABCWY

See Section 5.3.2.1, with the difference in the estimate statement:

```
PROC GENMOD data=dataset descending;
class trtgrp strain region agecat previousACWY subject_id ;
model outcome = trtgrp strain region agecat previousACWY / dist= bin
link= log DSCALE ;
repeated subject = subject_id / type= CS withinsubject= strain ;
estimate 'MenABCWY-ACWY' trtgrp 0 0 1 1 1 -3/ alpha=0.025 exp
divisor=3;

/*trtgrp T, U, and V are the ABCWY-1, ABCWY-2, and ABCWY-3 lots and
trtgrp W is ACWY*/
run;
```

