##### 5.4.2.2. Effectiveness by each of the endemic US *N. meningitidis* serogroup B strains

The SAS code to analyse the Vaccine effectiveness (Test-based): rMenB+OMV NZ - 3 doses (0,2,6-months schedule) by strain is specified below. Treatment, and randomization factors (i.e. region (US/ex-US), age category (10-17 YoA/18-25 YoA), previous MenACWY vaccination (y/n)) will be modelled as fixed effect. To account for a possible over-dispersion, the DSSCALE option in the model statement will be evaluated first. The DSSCALE will be kept in the model only if the F-statistics for the DSSCALE parameter is significant ( $p < 0.05$ ). The following SAS code will be used for the VE calculation:

```

ods trace on;
ods output GEEEmpPEst = genmod_stats
CONVERGENCESTATUS = converge ;

PROC GENMOD data=dataset descending;
class trtgrp region agecat previousACWY;
by strain ;
model outcome = trtgrp region agecat previousACWY / dist= bin link= log
DSCALE alpha=0.05;
estimate 'MenB026-ACWY' trtgrp 1 0 0 0 0 -1/ alpha= 0.05 exp;

/*trtgrp R is MenB0,2,6 and trtgrp W is ACWY*/

run;

ods output close;

data genmod_stats;
set genmod_stats;
by strain ;
where parm = 'trtgrp' and levell = '1';
rr = exp(estimate);
ub = exp(uppercl);
ve = (1 - rr)*100 ;
ve_ll = (1 - ub) * 100 ;
if ve_ll > 65 then success = 1 ;
else success = 0 ;
run;

```

where outcome represents the Bernoulli distributed outcome without bactericidal activity at a 1:4 dilution (i.e. response is 1 if titre < 4, and 0 if titre  $\geq$  4), one month after the 3rd vaccination in MenB0,2,6 and one month after the MenACWY vaccination for the ACWY arm, trtgrp indicates the vaccine groups, strain is the serogroup B strain variable, region is either US or ex-US, agecat is the age at enrolment (10-17 YoA or 18-25 YoA), and previousACWY is previous ACWY vaccination (y/n) at enrolment.

rr is the relative risk (RR), which is obtained from the estimated parameters from PROC GENMOD. Vaccine effectiveness (VE) is then derived as (1-rr)x100%.

ub represents the upper bound of the 95% CI of the relative risk. ve\_ll is the lower bound of the 95% CI for VE, if the value is greater than 65%, then the Vaccine effectiveness (Test-based): rMenB+OMV NZ - 3 doses (0,2,6-months schedule) objective is successful.

In summary in case of convergence issue the following hierarchical decision tree will be applied

- Binary model including region, agecat, and previousACWY
- Binary model, excluding region, agecat, and previousACWY

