## **6. ANALYSIS INTERPRETATION**

Multiple objectives and endpoints require type I error control. Full alpha (0.05) is split equally ( $\alpha=0.025$ ) between rMenB+OMV NZ objectives and MenABCWY objectives. Furthermore, within rMenB+OMV NZ, as well as within MenABCWY, objectives are tested hierarchically. If the first null hypothesis is rejected, then the testing will continue with the second hypothesis at same alpha. Same for 3rd, 4th, and so forth. Whenever a null hypothesis is not rejected, then the testing will stop.

As the comparator for MenABCWY non inferiority objective for the B component will be the selected schedule of rMenB+OMV NZ as determined in this study, the objectives of rMenB+OMV NZ will be analysed first. Additionally, if all null hypotheses related to rMenB+OMV NZ objectives will be rejected, the alpha ( $\alpha=0.025$ ) will be propagated to the MenABCWY part, and hypotheses related to MenABCWY objectives will be tested at full alpha ( $\alpha=0.05$ ). See Figure 2 for an explanation of the hierarchical testing (top to bottom, the order indicated by the arrows).

**Figure 2** Hierarchical testing of hypothesis

\* Alpha split equally between rMenB+OMV NZ and MenABCWY vaccine objectives.

If all rMenB+OMV NZ objectives achieved, MenABCWY vaccine objectives will be tested at full alpha.

\*\* If all objectives of rMenB+OMV NZ are met, the comparator will be the 0,2-months schedule. If the 0,2-months objective is not met, and the 0,6-months is met, then the 0,6-months schedule will be the comparator. If the 0,6-months is also not met, then the 0,2,6-months schedule will be the comparator.

Refer to Glossary of terms for definitions of test-based and responder-based vaccine effectiveness.

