#### **5.3.2.3. Vaccine effectiveness (Test-based): rMenB+OMV NZ - 2 doses (0,6-months schedule)**

See Section [5.3.2.1](#), with the difference in the treatment arm:

```
PROC GENMOD data=dataset descending;
class trtgrp strain region agecat previousACWY subject_id ;
model outcome = trtgrp strain region agecat previousACWY / dist= bin
link= log DSCALE ;
repeated subject = subject_id / type= CS withinsubject= strain ;
estimate 'MenB06-ACWY' trtgrp 0 1 0 0 0 -1/ alpha=0.025 exp;
/*trtgrp S is MenB0,6 and trtgrp W is ACWY*/
run;
```

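### The Amendment 4 SAS code for the primary VE reads the wrong GENMOD table: as written it returns no result, repaired only at the filter it applies 95% instead of 97.5% limits, and it cannot return the pooled MenABCWY estimate

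*SAP*

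**What the plan says.** The decision rule is clear. SAP section 6 states: "Full alpha (0.05) is split equally", which gives 0.025 to each vaccine family. Section 5.3.1.1 requires the lower limit of the two-sided 97.5% CI for VE to exceed 65%.

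Section 5.3.2.1 of Amendment 4 then prescribes SAS code for the calculation. Its parts are:

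- The MODEL statement has no `alpha=` option.
- The contrast is "estimate 'MenB026-ACWY' trtgrp 1 0 0 0 0 -1/ alpha=0.025 exp". The comment beside it identifies R as MenB_0_2_6 and W as ACWY.
- ODS OUTPUT captures the GEE parameter-estimate table. The ESTIMATE results are not captured.
- The data step keeps "where parm = 'trtgrp' and level1 = '1", exponentiates the estimate and upper limit from that table, and sets the success flag at 65%.
- The text below the code says: "ub represents the upper bound of the 97.5% CI of the relative risk".

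For MenABCWY, section 5.3.2.9 refers back to 5.3.2.1 and changes only the contrast: "estimate 'MenABCWY-ACWY' trtgrp 0 0 1 1 1 -3/ alpha=0.025 exp", with a divisor of 3. The lots are T, U and V.

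The same output request, filter and ESTIMATE-only alpha stand in Amendments 2 and 3. In Amendment 1, `alpha=0.025` stood on the MODEL statement.

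**The concern.** The confidence level is set on one statement and the result is read from another. The option moved from MODEL to ESTIMATE after Amendment 1, but the table that the data step reads did not change. The limit that the text calls the 97.5% bound is therefore not one.

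This code sets the success flag for primary objectives that do more than stand alone. If all rMenB+OMV NZ objectives are met, alpha passes to MenABCWY. Those objectives also determine which rMenB+OMV NZ schedule becomes the comparator for the MenABCWY non-inferiority test. Text and code that give different rules leave the programmer to choose between them once data are available.

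**Working it through.** **Plan's own figure.** 0.05 / 2 = 0.025 per family, i.e. a two-sided 97.5% CI. This agrees with sections 5.3.1.1 and 6.

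**Step 1: the code as written.** The comments in sections 5.3.2.1, 5.3.2.3 and 5.3.2.9 name six levels of `trtgrp`: R, S, T, U, V, W. None equals 1, so zero rows pass the filter and no success flag is set. The SAP describes no numeric recoding. If there were one, the inherited filter would return the first group, MenB_0_2_6, for the 0,6 and MenABCWY objectives as well.

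**Step 2: only the filter repaired, to R.** W is the last level and hence the reference, so the R parameter equals the R − W contrast and the point estimate is right. The limits follow the MODEL alpha. With none given, they are 95% limits. That default is GENMOD behaviour, not a statement in the SAP; the placement of alpha on MODEL in Amendment 1, and still in the by-strain code of Amendment 4, fits it.

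| | Required | From parameter table |
|---|---|---|
| Two-sided alpha | 0.025 | 0.05 |
| z | 2.241 | 1.960 |
| One-sided error at VE = 65% | 0.0125 | 0.025 |

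The half-width ratio is 2.241 / 1.960 = 1.14.

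**Step 3: size on the VE scale.** Success needs RR × exp(z × SE) < 0.35, so the smallest passing VE is 1 − 0.35 × exp(−z × SE). The SAP text at hand gives no SE(log RR), so the values below are assumptions.

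| Assumed SE | z = 1.960 | z = 2.241 | Gap, points |
|---|---|---|---|
| 0.03 | 67.00% | 67.28% | 0.28 |
| 0.06 | 68.88% | 69.40% | 0.52 |
| 0.10 | 71.23% | 72.03% | 0.80 |

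Example at SE 0.06 and observed VE 69.14% (RR 0.3086): the 95% lower limit is 1 − 0.3086 × exp(1.960 × 0.06) = 65.3%, a success. The 97.5% lower limit is 1 − 0.3086 × exp(2.241 × 0.06) = 64.7%, a failure.

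A plausibility check on the SE uses the planned 684 and 137 evaluable subjects and 35 strains each (sections 3.3 and 5.3.1.1). It assumes RR = 0.30, a control not-killed proportion p0 of 0.70 to 0.95, p1 = 0.30 × p0, and a within-subject correlation of 0.1 to 0.5. With DE = 1 + 34 × ICC,

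SE² = DE × [(1 − p1)/p1 / (684 × 35) + (1 − p0)/p0 / (137 × 35)],

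which gives SE from 0.023 (p0 0.95, ICC 0.1) to 0.067 (p0 0.70, ICC 0.5).

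**Step 4: MenABCWY.** The target is (T + U + V)/3 − W. The parameter table has one row per group, so no row holds this contrast, whatever level is chosen in the filter. It exists only in the ESTIMATE output, which the code never captures.

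**The case against.** The strongest reply is that the rule itself is not in doubt. Section 5.3.1.1 fixes 97.5%, the text under the code repeats it, alpha of 0.025 is on ESTIMATE, and nothing authorises a 95% decision for rMenB+OMV NZ. A careful programmer would notice. That is true, and it means that the alpha plan has not been changed. It does not cure prescribed code that applies another limit and cannot deliver a primary estimate.

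Several limits to the point stand:

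- A reader might infer that the code as written declares success at twice the allotted alpha. It does not. Run literally it returns nothing, which is at least visible. The doubled alpha appears only once the filter is repaired and the table is not. That is the natural quick repair, and it runs without warning.
- A reader might infer that the 0,6 objective would show a VE near zero, because Amendment 4 prints five coefficients for six groups, "estimate 'MenB06-ACWY' trtgrp 0 1 0 0 -1/ alpha=0.025 exp", while Amendment 3 prints six, "estimate 'MenB06-ACWY' trtgrp 0 1 0 0 0 -1/ alpha=0.025 exp". The documents do not support that. Amendments 1 and 3 have six and Amendments 2 and 4 have five, a pattern that may be a loss in text extraction. As long as the ESTIMATE output is unread, the contrast cannot affect the result.
- For MenABCWY after propagation, 95% is the correct level (section 5.3.1.9), so the level error concerns the rMenB+OMV NZ objectives and the case without propagation.
- The responder-based tests use Clopper-Pearson 97.5% limits (section 5.3.1.2) and are not affected.
- Amendment 5 supersedes this text, and its section 5.3.2.1 is not in the part at hand.

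**Conclusion.** The point holds for the code in Amendment 4, and for the same code in Amendments 2 and 3. As written, the code yields no success flag. With only the filter repaired, the rMenB+OMV NZ test-based objectives would be judged at two-sided 0.05 instead of 0.025. On the VE scale this lowers the bar by about 0.3 to 0.8 percentage points over the assumed SE range of 0.03 to 0.10. The shift is small, but it applies to primary tests that govern alpha propagation and comparator choice. The MenABCWY primary VE cannot be obtained from this data step under any repair of the filter alone.

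The conclusion rests on three things outside the stated rule: GENMOD's default 95% level, the group codes in the comments being the actual values, and the assumed SEs. Whether the fault is still live depends on Amendment 5.

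A secondary matter is the by-strain code in section 5.4.2.2. It requests "ods output GEEEmpPEst = genmod_stats" but has no REPEATED statement, so that GEE table is not produced. It also carries over the 65% success flag, although Table 1 sets no criterion for the per-strain objective. Its alpha of 0.05 on MODEL matches its intended 95% CI, and it has no bearing on the primary type I error.

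**What to change.** First check whether Amendment 5 retains this code. If it does:

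1. Capture the ODS table Estimates and delete the `parm`/`level1` filter.
2. Select the row by contrast label (MenB026-ACWY, MenB06-ACWY, MenABCWY-ACWY) and take RR, its upper limit and VE from that row.
3. Use alpha 0.025 for rMenB+OMV NZ. For MenABCWY use 0.025, or 0.05 after propagation; the ESTIMATE statement in 5.3.2.9 currently hard-codes 0.025.
4. At the same time, confirm that the 0,6 contrast has six coefficients (`0 1 0 0 0 -1`). Once the Estimates table is read, this will matter.
5. In the by-strain code, read Estimates as well and remove the copied success flag.

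The cost is a few lines of SAP code. Design, data collection, sample size and the stated criteria do not change.
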